### 12.2.2 *Criteria related with ophthalmic ailments*

1. Serious tear film dysfunction syndrome
  - TBUT < 5 s
  - Schirmer: < 4 mm

- OSDI > 30 points
  - Corneal staining > grade III on the Oxford scale
2. Non perforated corneal ulcer
  3. Perforated corneal ulcer
  4. Autoimmune corneal ulcer
  5. Ocular surface scarring diseases
  6. Ocular surface or annexes metaplastic lesions
  7. Fibro vascular proliferation lesions on the conjunctival and/or corneal surface (i.e.: pterygium)
  8. Concomitant chronic inflammatory diseases on any ocular structure
  9. Acute or infectious inflammatory disease
  10. Corneal disease potentially requiring a treatment during the following 3 months
  11. Use of topical or systemic drug products classified as forbidden
  12. Ocular surgical procedures 3 months before the protocol inclusion
  13. Treatments or procedures indicated on the tear film dysfunction treatment, as punctal silicone plugs.
  14. Posterior segment diseases requiring a treatment or threatening the visual prognosis
  15. Retinal diseases potentially requiring treatment during the following 3 months
  16. History of penetrating keratoplasty.
  17. Soft or hard contact lenses use during the last month from inclusion day

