### 13.2 OSDI

The sample size was calculated according to the formula for continuous quantitative variables:

With a statistical confidence level of 95%, which corresponds to the error type I, and is equal to 1.96, with a potency of 80% corresponding to the error type II, and is equal to 0.84, a standard deviation for the 6.4 points increase in score OSDI, with an expected difference of at least 6.1 points, was considered.

Based on the above, the result was 34 patients, which increased 20% in consideration of the losses, with a total of 41 patients per group, with total study population of 123 subjects (246 eyes).

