#### 14.1.2 Efficacy Assessment Parameters

Parameters	Value
Best-corrected visual acuity	Increase of 1 line in the Snellen chart or 1 logarithmic point (logMAR)
Corneal depithelization	Percentage of the damaged epithelium of the ocular surface, reduction of staining according to the oxford scale.
Tear film break-up time	Increase in the residence of the teal film, measured in seconds. Increase of 30% from baseline or equal or more than 10 sec.
Schirmer test	Increase of more than 30%
Adverse events	Presence of adverse events modifying some of the abovementioned criteria or others, evaluated as serious.
OSDI	Reduction of 20% of the total score from the baseline score.
Goblet cells population	Increase of 20% from baseline

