#### 14.3.1 Safety Parameters

Parameters	Value
Best-corrected visual acuity	No change of 1 line in the Snellen chart or 1 logarithmic point (logMAR)
Intraocular pressure	Measurements below 7 mmHg and over 21 mmHg
Corneal depithelization	Percentage of the damaged epithelium of the ocular surface, reduction of staining according to the Oxford scale.
Anterior segment examination	Abnormalities on any of the comprised structures: Cornea, iris, pupil, iris-corneal angle and crystalline.
Posterior segment examination	Abnormalities on any of the comprised structures: Vitreous, retina, macula and optic nerve.
Tear film break-up time	Reduction of more than 20% over the baseline time.
Schirmer test	Reduction of more than 20%
Adverse events	Presence of adverse events modifying some of the abovementioned criteria or others evaluated as serious.
OSDI	Increase of the score of more than 10 points.

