Answer the following questions by circling the box which best represents your answer:

1. Have you experienced any of the following during last week?

	FREQUENCY				
	All of the time	Most of the time	50% of the time	Some of the time	None of the time.
Eyes that are sensitive to light.	4	3	2	1	0
Eyes that feel gritty.	4	3	2	1	0
Painful or sore eyes.	4	3	2	1	0
Blurred vision.	4	3	2	1	0
Poor vision.	4	3	2	1	0
Subtotal:					

2. Have problems with your eyes limited you in performing any of the following during last week?

	FREQUENCY				
	All of the time	Most of the time	50% of the time	Some of the time	None of the time.
Reading.	4	3	2	1	0
Driving at night	4	3	2	1	0
Working with a computer or bank machine (ATM)	4	3	2	1	0
Watching TV	4	3	2	1	0
Subtotal:					

3. Have your eyes felt uncomfortable in any of the following situations during last week?

	FREQUENCY				
	All of the time	Most of the time	50% of the time	Some of the time	None of the time.
Windy conditions.	4	3	2	1	0
Places or areas with low humidity (very dry).	4	3	2	1	0
Areas that are air conditioned.	4	3	2	1	0
Subtotal:					

OSDI score= total score × 25 / number of answered questions

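### The OSDI form does not say how to record an item that did not apply in the past week: a circled 0 and a blank score differently, enough to move a subject across the entry limit and, with three or more items, to meet the response rule

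*Combined protocol and SAP*

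**What the plan says.** The questionnaire at the end of Section 21 has 12 items in three blocks: five symptoms, four activities and three situations. Its completion instruction is "Answer the following questions by circling the box which best represents your answer". All three blocks carry the same five boxes, 4 down to 0. The second block asks "Have problems with your eyes limited you in performing any of the following during last week" and lists reading, night driving, computer or ATM use, and television. The third asks "Have your eyes felt uncomfortable in any of the following situations during last week" and lists wind, low humidity and air conditioning. The score is "OSDI score= total score × 25 / number of answered questions".

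The score is then used in four places:
- Section 12.1 admits subjects below 30 points, with no lower limit.
- Section 12.2.2 excludes serious disease, including "OSDI > 30 points".
- Section 14.1.2 sets the efficacy change as "Reduction of 20% of the total score from the baseline score".
- Section 14.3.1 lists as a safety change "Increase of the score of more than 10 points".

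The form is given at five visits (Section 9). The visit procedures in Section 11 and the analysis in Section 15 give no rule for unanswered items, for a minimum number of answers, or for keeping the same items across visits.

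**The concern.** Dividing by the items answered means that some items may go unanswered. The form, however, has no box for an item that did not apply and no instruction to skip one. A subject who did not drive at night or meet dry air that week can reasonably circle 0 or leave a blank, and the scoring rule treats the two differently. Ages run to 90 and recall is one week, so which items apply can vary between subjects and between visits in one subject.

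Two things are at stake. Entry can depend on how such an item was recorded. Change from baseline can also mix two denominators, so part of it may come from recording. A circled 0 cannot be sorted out afterwards: it does not show whether the subject had no difficulty or did not do the activity.

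**Working it through.** The protocol states no figure for this effect, so its own formula is applied directly.

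**Inputs.** Score = 25 × S / A, where S is the sum of circled values and A the number of items answered (Section 21). With all 12 answered at 4, the score is 48 × 25 / 12 = 100. The thresholds are entry below 30 (Section 12.1), a 20% fall (Section 14.1.2) and a rise above 10 points (Section 14.3.1). The number of items not met, k, is not in the documents. It is an assumption, shown from 1 to 4; blocks 2 and 3 together hold seven items.

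**Size of the shift.** With S fixed, blank coding gives 25S/(12 − k) and zero coding gives 25S/12. The ratio of zero to blank coding is (12 − k)/12.

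| k | Blank to 0 | 0 to blank | Item sums below 30 only when coded 0 |
|---|---|---|---|
| 1 | −8.3% | +9.1% | 14 |
| 2 | −16.7% | +20.0% | 12 to 14 |
| 3 | −25.0% | +33.3% | 11 to 14 |
| 4 | −33.3% | +50.0% | 10 to 14 |

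**Entry.** One item is enough. For S = 14 and k = 1, a blank gives 14 × 25 / 11 = 31.8 (excluded) and a 0 gives 14 × 25 / 12 = 29.2 (eligible). With k = 3, the blank-coded score is 14 × 25 / 9 = 38.9 against the same 29.2. No inconsistency between visits is needed.

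**Response.** For recoding alone to give a 20% fall, (12 − k)/12 must be at most 0.80, so k must be at least 2.4, which means three items. All three must go from blank at baseline to 0 later.
- S = 9, k = 3: 9 × 25 / 9 = 25.0 becomes 9 × 25 / 12 = 18.75, a 25% fall.
- S = 10, k = 3: 27.8 becomes 20.8, a fall of 6.9 points. For scale, Section 13.2 plans "with an expected difference of at least 6.1 points".
- Two items do not reach 20%. A real fall in item sum of 1 − 0.80 × 12/10 = 4.0% is still needed. One item leaves 1 − 0.80 × 12/11 = 12.7%.

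**Safety.** An eligible subject with all 12 items answered has S of at most 14, since 15 × 25 / 12 = 31.25. Moving k items from 0 to blank at S = 14 adds 38.9 − 29.2 = 9.7 points for k = 3, which is not above 10. For k = 4 it adds 43.75 − 29.17 = 14.6 points.

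**Consistent coding.** If the same items are always blank or always 0, the denominator cancels in the percent change. Unchanged item scores then give exactly 0%.

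**How few subjects matter.** Section 14.1 judges PRO-087 effective on changes in more than 5% of subjects, and the safety statement before Section 14.3.1 uses the same cut. With 96 per group (Section 13.3), 5% is 4.8. With the 80 before allowance for losses, it is 4.0. Five subjects exceed the cut in either case.

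**The case against.** The other side has a good deal of weight:

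- Recoding alone gives a false response only when at least three items change the same way between visits. A subject who never drives and records it alike each time produces no artefact in percent change. This stands.
- OSDI is one of four entry limits in Section 12.1 and one of six efficacy variables in Section 14.1, and Schirmer sets the sample size. OSDI appears in the Section 14.3.1 table but not in the numbered list of safety variables before it. The entry effect is confined to a narrow band of item sums. This also stands.
- The trial is randomised and described as double-blind, so recording errors should fall on all arms alike. That holds for comparisons between arms, where the cost is noise. It does not protect an entry limit or a 5% count taken within the PRO-087 arm.
- A one-line instruction would settle the coding without changing the form. That would work, but a blank would then not distinguish an item that did not apply from one overlooked.

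A reader might go further and infer that the form understates severity, so that subjects who are truly too severe get in. The documents do not say which coding is correct. The formula mentions answered items, not applicable ones, and for a non-driver the zero box in block 2 is literally true. A reader might also take 25% as the effect of one activity, or as a ceiling. It is the three-item case: one item gives 8 to 9%, and four give 33% down or 50% up.

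**Conclusion.** The concern holds in a limited form. The scoring rule and the form do not fit together, because the coding of an item not met in the past week is undefined and the two natural entries give different scores. One such item can decide entry near 30 points. At least three must change from blank to 0 to meet the 20% response rule without symptom change, and four from 0 to blank to breach the 10-point safety rule from a fully answered eligible baseline.

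It would be tempting to conclude that one subject could both enter and respond falsely because of the same items. The arithmetic rules this out: false entry needs zeros at baseline, and false response needs blanks there. Nor do the documents support a claim that the flaw favours PRO-087 over the comparators.

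These results assume an unchanged item sum and the values of k shown. How many subjects have such items, and how often their recording would change, is not in the documents. The exposure is the entry limit, the within-arm 5% criteria and added noise. Severity is minor to moderate.

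**What to change.** Before the form is used:
1. Add a not-applicable box, counted as unanswered, to the seven items in blocks 2 and 3, with an instruction to use it the same way at every visit.
2. State in the derivation the minimum number of answered items for a valid score.
3. Derive the 20% and 10-point changes from items answered at both baseline and the visit in question, with the same denominator at both, at least as a sensitivity analysis.

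The cost is one column on the form and a short derivation rule. The drawbacks are that the change score rests on fewer items in some subjects, and that a subject's baseline value may differ between visit comparisons because the shared items differ. If that is unwelcome in the main analysis, item 3 can stay a sensitivity analysis, provided item 1 is in place from the first subject.
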